### Primary hypothesis tests, with adjustment for multiple comparisons

Our primary hypothesis tests will be 3 pairwise comparisons:

- Test 1: Arm 1 vs Arm 2
- Test 2: Arm 1 vs. Usual Care
- Test 3: Arm 2 vs. Usual Care

In order to maintain an overall type 1 error rate of 5%, we will set our critical p-value threshold for Test 1 at  $p=0.04$ , and then at  $p=0.005$  for Test 2 and Test 3 since they will benefit from the very large sample size expected in the Usual Care groups. No other adjustments for multiple comparisons are planned for secondary outcomes or other exploratory analyses described below.

**Descriptive analyses comparing clinic-level baseline characteristics:** *Descriptive statistics* will be used to compare clinic-level characteristics between the two intervention arms at baseline. We will include descriptions of clinic-level patient population characteristics (age groups, gender, race/ethnicity, type of insurance, mean number of current antihypertensive medication classes prescribed, and prevalence of comorbid conditions such as diabetes, chronic kidney disease, or heart failure), workforce composition (i.e. proportion of nurse practitioners, physician assistants, physicians, and physician specialty - internal vs family medicine), clinic size and staffing level (total number of patients, nurses, and medical assistants), level of access (availability of same-day appointments, mean time to third next available appointment), and possibly other characteristics depending on availability.

**Sensitivity analyses:** In a sensitivity analysis, we will perform multivariable linear regression analyses to compare clinic-level pre-post differences in our primary and secondary outcomes. The regression models will adjust for health system as well as for whether the clinic was engaged in BP HOME, a concurrently running individual-level randomized trial that will provide home blood pressure monitoring devices to participating patients with a high blood pressure reading in clinic. We will also consider linear mixed models (LMMs) for repeated changes in the summary outcome measures, adjusting for age, sex and race-ethnicity. In particular, for each clinic we will calculate monthly values of the metric  $(t_i - t_0)$ , for follow-up month  $i = 1, \dots, 6$ , within strata jointly defined by age, sex, and race-ethnicity, as well as corresponding within-stratum weights as described above, then estimate the effect of treatment adjusted for stratum, using an LMM that includes treatment assignment, month as categorical, the interaction of these two factors, and stratum. With a view towards model simplification, likelihood ratio testing will be used to determine whether age, sex, and race/ethnicity as additive factors adequately capture the stratification effects. We will: (1) present month-specific treatment effects with 95% confidence intervals (CIs); (2) test for heterogeneity in the monthly treatment effects across months; (3) summarize the treatment effect by the average of the month-specific effects also with a 95% CI, if the test for heterogeneity is not statistically significant ( $P>0.05$ ); and (4) otherwise, use orthogonal contrasts to check for linear and quadratic trends in the monthly effects.

**Subgroup analysis to test for heterogeneity of treatment effects (HTE):** We will produce clinic-level subgroup-specific analyses limited to subgroups defined by the characteristics listed in Table 3 (with imputation as described above), and test for interactions by intervention group (as well as with Usual Care) and subgroup categories. We hypothesize that the BP Control effect from the Full-Support intervention relative to Self-Guided and Usual Care groups will be smaller in patients who are younger, male, and Black given published BP control difficulties in these patients. We will also specifically test for an interaction between treatment group and enrolling CDRN, given health IT infrastructures may differ by CDRN in ways that can interact with the effectiveness of the interventions. All subgroup analyses will be reported.

**Table 3. Subgroups for HTE analysis**

Age: 18-44 vs. 45-64 vs. 65+

Race/ethnicity: NH White vs. NH Black vs. NH Asian vs. Hispanic (any race) vs. Other
Sex: Male vs. Female
Enrolling CDRN
HTE – Heterogeneity of treatment effects
NH – Non-Hispanic

**Exploratory Mediation analysis:** As many of our secondary outcomes are presumably process measures in the causal pathway to achieving BP control, we will perform a mediation analysis to understand the degree to which the potential added benefit of the Full Support intervention on BP control is explained by changes in the process measures. We will perform a mediation analysis using nested linear regression models for the effect of randomization assignment (i.e. Full Support vs. Self-Guided) on clinic level pre-post differences in percent control, first omitting, then adding each of our proposed mediators to the base model. The hypothesized process mediators will include pre-post changes in BP measurement accuracy, medication intensification, and average SBP reduction after medication intensification, and repeat visit in 4 weeks after uncontrolled HTN. These analyses will be implemented using the Paramed module in Stata statistical software  to calculate natural direct effect (NDE) of full-support on BP control and the natural indirect effect (NIE) through each mediator. The total causal effect (TCE) is the sum of the NDE and NIE. Dividing each NIE by the TCE will calculate the proportion of the causal effect explained by each mediator.

**Additional exploratory analyses:** We will explore temporal patterns in the effect of randomization assignment using linear mixed models for repeated clinic-level changes since baseline in primary and secondary outcomes assessed at 6, 12, and 18 months. These models will include random effects for clinic, as well as fixed effects for treatment assignment (as a categorical variable), and their interaction. Heterogeneity of treatment effects across time will be tested using a 2 degree-of-freedom chi-square test; in addition, a chi-square test for linear trend will be obtained by comparing the fitted treatment assignment effects at 6 and 18 months.

**Data source, collection, management, and safety:** Consistent with principles of pragmatic clinical trials, we will use EHR data for patient identification and assessment of intervention implementation and outcomes. Both interventions (and usual care) are consistent with standard of care. Therefore, both the interventions and data collection in this study carry minimal risk to patients. We will leverage the data infrastructure and resources in the PCORnet Common Data Model to collect de-identified, clinic-level aggregate data needed for analysis. Additional details on the PCORnet Common Data Model procedures for data collection and linkage, and data management and safety are described elsewhere.

**Sample size and power:** Preliminary data from “Wave 2” implementation of the M.A.P. Program by AMA in 16 clinics shows average pre-post improvements (without a control group) in BP control of 6.8% (65.6%-->72.4% overall) +/- 4.4% (standard deviation of change in control rate). Assuming negligible change in the Self-Guided arm, standard sample size calculations show that we will have 83% power to detect a difference in differences of 6% in the BP control rate (or 92% power for 7% difference) between Self-Guided and Full-Support arms with 10 clinics randomized to each arm of the study; these results were confirmed using simulations. Power will be higher for comparisons of the Self-Guided and Full-Support groups with the large Usual Care comparison group in PCORnet under similar effect-size

assumptions. For the HTE analysis comparing the difference in differences between the 10 clinics in CDRN 1 (5:5 in each arm) and the 10 clinics in CDRN 2 (5:5 in each arm), we expect to have 80% power to detect an interaction effect (i.e., the difference in the difference in differences) of 12% in the BP control rate. Corresponding minimum detectable interaction effects would be 15%, 13%, and 12% for demographic subgroups comprising 20%, 30%, and 40% of the overall population.

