### **Randomization**

We will use a random number generator to randomize 10-14 Active Clinics to the Full Support Arm and 10-14 Active Clinics to the Self-Guided Arm. Randomization will be stratified (and balanced within strata) by CDRN and by participation (or not) in BP HOME, a concurrently running individual-level RCT that will provide home blood pressure monitoring devices to participating patients with a high blood pressure reading in clinic. As this is a real-world intervention that clinics will have to implement, they will not be blinded to the randomization.

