### **Analysis Plan**

Overview: We will use an unadjusted difference-in-differences analytic approach to testing comparative effectiveness hypotheses, weighting for differences in cluster size. Despite expected between-clinic differences in baseline characteristics and BP control (especially in the non-randomized comparison with Usual Care control organizations), the difference-in-differences approach provides some protection against confounding because the outcome being compared is a within-clinic change score, as described below. We will first conduct 3 pairwise primary hypothesis tests (adjusting for multiple comparisons), as described below. We will then conduct a series of exploratory analyses of secondary outcomes, sensitivity analyses adjusting for baseline clinic-level characteristics, subgroup analyses to examine heterogeneity of effect, and exploratory mediation analyses to understand the mechanisms by which the full-support intervention might provide greater effectiveness.

Differences-in-differences analytic approach: We will calculate difference-in-differences through the following steps:

1. Use clinic-level metrics (e.g., % BP control) at baseline for each clinic before the intervention starts ( $t_0$ ) and then including the 6th full month of the intervention (" $t_6$ ", noting that the period will actually be 7 months offset for the Intervention Clinics and 6 months for the Usual Care Clinics; see Outcomes and Measurements, above)
2. Calculate the clinic-level pre-post difference in the metric ( $t_6 - t_0$ )
3. Calculate the mean pre-post difference in each treatment group, the between-group difference of differences, both with 95% confidence intervals, and compare the 20-28 pre-post differences by arm using weighted linear regression; observations will be weighted by the inverse of the site-specific variances of the change scores, which will be approximated using the site-specific sample size and level of the time-specific metrics, and the average correlation of the pre- and post-metrics across clinics. Weights will be normalized to sum to the total number of clinics in the Arm 1 vs. Arm 2 comparisons (and to the number of included clinics plus the number of participating PCORnet datamarts for the comparisons of each Arm with Usual Care).

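### The exploratory mediation analysis computes a share explained whatever the size or precision of the total effect, and names no covariate for the mediator-outcome relation

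*Combined protocol and SAP*

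**What the plan says.** The paragraph on exploratory mediation analysis (Analysis Plan, after Table 3) uses nested linear regressions, with arm (Full Support or Self-Guided) as the exposure and each clinic's change in % control as the outcome. It describes the sequence of models as "first omitting, then adding each of our proposed mediators to the base model". The mediators are themselves change scores: "The hypothesized process mediators will include pre-post changes in BP measurement accuracy, medication intensification, and average SBP reduction after medication intensification", together with repeat visits after an uncontrolled reading. The plan then estimates a natural direct effect and "the natural indirect effect (NIE) through each mediator", and ends with a ratio: "Dividing each NIE by the TCE will calculate the proportion of the causal effect explained by each mediator".

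The paragraph mentions no covariate, no assumption about confounding of mediator and outcome, no interval for the ratio, and no minimum size or precision for the total effect.

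The Analysis Plan overview states: "We will use an unadjusted difference-in-differences analytic approach to testing comparative effectiveness hypotheses". Covariates appear under Sensitivity analyses, for the primary and secondary outcomes: "The regression models will adjust for health system as well as for whether the clinic was engaged in BP HOME". Both stratification factors are known for every clinic: "Randomization will be stratified (and balanced within strata) by CDRN and by participation (or not) in BP HOME".

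**The concern.** There are two separate problems, and both arise even with a single mediator.

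**The ratio.** NIE/TCE is formed unconditionally. With 20-28 clinics its denominator can be close to zero or negative. A percentage would then be printed for every process measure even if the trial showed no difference between Full Support and Self-Guided.

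**The mediator-outcome relation.** Randomisation protects the effect of arm on the mediator and of arm on the outcome. It does not protect the relation of mediator to outcome, because clinics are not randomised to a level of process change. Natural direct and indirect effects need that relation to be free of confounding. Outcome and mediators are all changes, and a clinic's starting level may influence both. If so, a process measure with no effect on BP control can be given a non-zero share, positive or negative.

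At stake is the account of how Full Support might work, not whether it does.

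**Working it through.** **Inputs from the plan.** SD of clinic-level change 4.4 points, 10 clinics per arm, target difference 6 points (Sample size and power); 10-14 clinics per arm (Randomization).

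**Assumptions, because the documents give no figures.** The mediator is raised 8 points by arm, has a within-arm SD of 6 and no effect on BP control. The correlations in step 5 are also assumed.

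1. *The plan's own figure.* SE of the total effect = 4.4 × √(2/10) = 1.97 points. Noncentrality is 6/1.97 = 3.05. A two-sided t-test on 18 df at 0.05 gives 82.2% power for 6 points and 92.0% for 7, against the stated 83% and 92%. The inputs are therefore read correctly. With 14 per arm the SE is 4.4 × √(2/14) = 1.66.

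2. *The denominator.* At a true effect of 3 points the estimate is negative with probability Φ(-3/1.97) = Φ(-1.52), about 6%. At a true effect of zero it is negative half the time.

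3. *The numerator.* NIE = arm coefficient without the mediator minus arm coefficient with it. For an inert, unconfounded mediator its true value is 0, and its sampling SD is roughly 8 × 4.4/(6 × √18) = 1.4 points. Half of a 3-point effect is 1.5 points, so a spurious share of 50% lies only about one standard error away.

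4. *Simulated share, 20 clinics, inert mediator, no confounding.*

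| True total effect | Trials with absolute share above 50% |
|---|---|
| 6 points | about 10% |
| 3 points | about 34-35% |
| 0 | about 59-60% |

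If the share is reported only when the 95% interval for the total effect excludes zero, the 3-point figure falls to about 9-10% of the trials that report one.

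5. *Baseline levels as a common cause (24 clinics, true effect 6).* Let each change correlate with its own baseline (r_Y, r_M) and the two baselines correlate r_B. The within-arm correlation of the changes is ρ = r_Y × r_M × r_B, and the expected spurious NIE is (8/6) × ρ × 4.4.

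| r_Y, r_M, r_B | ρ | Expected NIE (points) | NIE/6 | Simulated median share |
|---|---|---|---|---|
| -0.5, -0.5, 0.5 | 0.125 | 0.73 | 12% | 11% |
| -0.5, -0.5, 0.7 | 0.175 | 1.03 | 17% | 16% |
| -0.3, -0.3, 0.3 | 0.027 | 0.16 | 3% | 2-3% |
| -0.5, -0.5, 0 | 0 | 0 | 0% | 0% |
| -0.5, -0.5, -0.5 | -0.125 | -0.73 | -12% | -11% |
| -0.7, -0.7, 0.8 | 0.392 | 2.30 | 38% | 37% |

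6. *Adjustment.* Adding the two baseline values brings the median to 0%. In the first row the 95% range moves from -0.36 to 0.77 (width 1.13) to -0.56 to 0.58 (width 1.14). With CDRN and BP HOME status also added, at 20 clinics, the range goes from about -0.45 to 0.91 (width 1.36) to about -0.75 to 0.78 (width 1.53).

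7. *Adjustment does not rescue the ratio.* In a separate run (10 per arm, mediator raised by 1 SD, true effect 2 points, the shared cause fully adjusted for), the share still had a 95% range of about -4 to +4. The two remedies do different work.

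**The case against.** The strongest reply is that this is a labelled exploratory analysis on which no primary or secondary effect estimate depends. That stands, and it sets the priority.

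Three stronger readings are tempting, and the documents do not support them.

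- *That the plan excludes covariates and fits one mediator at a time.* The base model is never defined, and the text is silent on covariates. The description as unadjusted is attached to the comparative effectiveness tests. Adding each mediator could mean cumulative entry, although one NIE and one proportion per mediator point to separate models. The plan also cites a methods paper on the assumptions of mediation analysis, but does not say how those assumptions will be met. What can be said is that the covariate set is unspecified.
- *That inert measures will be credited with part of the effect.* The direction depends on correlations the documents do not give. If the baselines are uncorrelated there is no bias from this source. If they are negatively correlated, the share is pushed down and a real mediator could be hidden. The 37% figure needs three strong correlations at once.
- *That adjusting for everything available cures the problem.* In the first row of step 5, all four covariates left absolute shares above 50% about as common as before: 13% against 12% at 20 clinics, 8% against 9% at 24. Adjustment centres the estimate but does not make it precise. Nor does baseline adjustment remove other shared causes, such as another process measure moved by the same programme.

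None of this touches the ratio: under any reading it is computed without a condition or an interval.

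**Conclusion.** The point holds, more firmly for the ratio than for the confounding.

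**Ratio.** The standard error of 1.97 points follows from the plan's own SD and clinic numbers. The proportions of about 10%, a third and 60% also rest on the assumed mediator shift of 8 points with SD 6. Unless the true effect is near the planned 6 points, the shares cannot be interpreted as the plan stands.

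**Confounding.** The gap is real in principle because nothing is specified to protect the mediator-outcome relation. Its size and sign are unknown: a median share of about -11% to +16% for an inert measure under moderate assumed correlations, 37% in an extreme case, and about 0 with uncorrelated baselines.

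A reader might infer that the trial's main result is in doubt. It is not: the primary comparison uses none of these models. This is a low-priority change to an exploratory analysis.

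**What to change.** Amend the mediation paragraph as follows.

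1. Report NIE and NDE in percentage points with bootstrap intervals. Report NIE/TCE, with its own interval, only when the interval for the total effect excludes zero at the level used for Test 1 (0.04, so a 96% interval).
2. Include baseline % BP control and the baseline value of the mediator concerned in both the mediator model and the outcome model. Add CDRN and BP HOME status as a sensitivity analysis only, given 20-28 clinics.
3. Define the base model, and say whether mediators enter singly or cumulatively.
4. State that residual mediator-outcome confounding remains possible.

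**Cost.** SAP wording only, since the baseline metrics and stratification factors are already held. The main models lose two degrees of freedom. No shares are reported if no total effect is shown. The total effect in these models is baseline-adjusted, so it will not match the unadjusted primary estimate exactly and should be labelled accordingly.

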The AMA developed a framework for clinic-based quality improvement that works within traditional office-based configuration of healthcare delivery (the “Measure Accurately, Act Rapidly, and Partner with Patients” (M.A.P.) Program, described below). The AMA is collaborating with AHA in the initiative, “Target:BP” to 1) recognize health care organizations achieving  $\geq 70\%$  BP control and 2) improve BP control by scaling the M.A.P. program to build a healthier nation. The initiative includes a set of tools, resources and detailed plans to support clinics interested in implementing the M.A.P framework as a structured intervention program.

Pilot implementation of this program led to dramatic improvements in BP control (from 63% to 90% in a single clinic and 64% to 74% in a group of 16 clinics). Although these results are promising, questions remain regarding how to optimize and efficiently scale the program in order to maximize sustained clinic-level involvement remain.

In this study, we will randomize 20-28 clinics to receive one of two types of support interventions: 1) a set of self-evaluation tools, improvement plans, and other resources that can be accessed by clinics and used independently (“Self-Guided”), and 2) a practice facilitation support program that helps clinics understand those tools/plans/resources and actually train people to implement the tools and plans (“Full Support”). We will then compare BP control between those arms, and against Usual Care control organizations. Additionally, we will perform a limited program evaluation to examine stakeholder satisfaction and assess barriers and facilitators to implementation as well as their willingness to continue program-related activities beyond the study period.

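### Chi-square tests of effect change over 6, 12 and 18 months are modestly anti-conservative with 20-28 clinics, by an amount that depends on an unstated covariance structure

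*Combined protocol and SAP*

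**What the plan says.** The Additional exploratory analyses paragraph, which follows Table 3 in the Analysis Plan, states: "We will explore temporal patterns in the effect of randomization assignment using linear mixed models for repeated clinic-level changes since baseline", for "primary and secondary outcomes assessed at 6, 12, and 18 months". On the model it says: "These models will include random effects for clinic, as well as fixed effects for treatment assignment (as a categorical variable), and their interaction". On testing it says "Heterogeneity of treatment effects across time will be tested using a 2 degree-of-freedom chi-square test" and, further, "a chi-square test for linear trend will be obtained by comparing the fitted treatment assignment effects at 6 and 18 months".

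The independent units are few. The Background states "In this study, we will randomize 20-28 clinics", and the Randomization section allocates "10-14 Active Clinics to the Full Support Arm and 10-14 Active Clinics to the Self-Guided Arm".

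The paragraph does not give the covariance structure, the estimation method (REML or ML) or a significance level. No F, t, Kenward-Roger, Satterthwaite or permutation reference for these models appears elsewhere in the document. The section on primary hypothesis tests plans no multiplicity adjustment for exploratory analyses.

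**The concern.** A Wald chi-square reference is a large-sample approximation: it ignores the uncertainty in the estimated variance components. Here they come from 18 to 26 between-clinic degrees of freedom (20 − 2 to 28 − 2). The Usual Care group does not help, because the tested effect is that of random assignment.

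The error runs in one direction: with no true change over time, the tests declare that the Full Support versus Self-Guided difference grows or fades more often than the nominal rate. They cover ten metrics (one primary, nine secondary) with two tests each. With 20 clinics and no true change, the expected number of false positives is 20 × 0.05 = 1.0 at the nominal level. The chi-square reference gives 10 × (0.063 + 0.058) = 1.2 with a random intercept and 10 × (0.087 + 0.066) = 1.5 with an unstructured covariance.

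**Working it through.** **Plan's own figure.** The document gives no error rate for these tests. The nearest figure is the power statement in Sample size and power: 83% for a 6-point difference and 92% for 7 points, with 10 clinics per arm and an SD of change of 4.4 points. The noncentrality is 6/(4.4 × √(2/10)) = 3.05, or 3.56 for 7 points. A two-sided 5% t test with 18 df then gives 82.2% and 92.0%; a normal approximation gives 86.2% and 94.5%. The planning figures are therefore close to a small-sample t reference for the same clinics, which the over-time tests do not use.

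**Inputs.**
- N = 20 or 28 clinics in two equal arms (Background; Randomization).
- Three times: 6, 12 and 18 months. Two arms by three times gives the 2 df that the plan names.
- Critical values at an assumed 5%: 5.991 (2 df) and 3.841 (1 df). The assumption follows the P>0.05 criterion attached to the monthly heterogeneity test in Sensitivity analyses ("if the test for heterogeneity is not statistically significant").
- Further assumptions: REML, equal weights, complete data.

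**Random intercept for clinic.** The within-clinic variance has 2(N − 2) df: 36 or 52.
- 2-df test: P[F(2, 36) > 5.991/2] = 0.063; P[F(2, 52) > 5.991/2] = 0.059.
- Trend: P[F(1, 36) > 3.841] = 0.058; P[F(1, 52) > 3.841] = 0.055.

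**Unstructured covariance over the three times.** The 2-df statistic is a Hotelling T², so its size is P[F(2, N − 3) > 5.991(N − 3)/(2(N − 2))].
- N = 20: 5.991 × 17/36 = 2.83; P[F(2, 17) > 2.83] = 0.087.
- N = 28: 5.991 × 25/52 = 2.88; P[F(2, 25) > 2.88] = 0.075.
- Trend: P[F(1, 18) > 3.841] = 0.066; P[F(1, 26) > 3.841] = 0.061.

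| Test | Covariance | 20 clinics | 28 clinics |
|---|---|---|---|
| Heterogeneity, 2 df | Random intercept | 6.3% | 5.9% |
| Heterogeneity, 2 df | Unstructured | 8.7% | 7.5% |
| Linear trend, 1 df | Random intercept | 5.8% | 5.5% |
| Linear trend, 1 df | Unstructured | 6.6% | 6.1% |

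Simulation with 200,000 trials per setting agrees with every entry to within 0.1 point. With ML in place of REML, the 2-df test is worse: about 8.1% to 7.1% (random intercept) and 10.8% to 8.9% (unstructured).

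**Overlapping windows.** Each metric uses a 12-month window, so windows that end six months apart share six months of data and serial correlation is plausible. As an illustration, take an AR(1) correlation of 0.5 to 0.9 (an assumption) and fit a random intercept. The trend test then has simulated size 9.0% to 11.5% with the chi-square reference, and still about 8% to 10.5% with the matching F reference. The 2-df test has 6.2% to 7.1% with chi-square. In that setting the covariance model is the larger source of error for the trend test.

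**The case against.** The strongest reply is that little is at stake. The analyses are labelled exploratory, no decision rule hangs on them, and multiplicity control is expressly not claimed. The most literal reading of clinic random effects is a random intercept, under which the excess is only 0.5 to 1.3 points. All of that stands.

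Four stronger readings are tempting, and the document does not support them.

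- A reader might quote a single true error rate of 6% to 9% for both tests. The upper part needs an unstructured covariance, which the plan does not mention, and the trend test, a single contrast, lies at 5.5% to 6.6%.
- A reader might infer that these tests settle whether the effect is sustained. The plan addresses sustainability through the survey and interviews of its limited program evaluation, and lists the 12- and 18-month changes separately as secondary outcomes.
- A reader might extend the chi-square criticism to the monthly mixed model in Sensitivity analyses. That paragraph names no reference distribution for its heterogeneity test. It does plan likelihood ratio comparisons of fixed stratum effects, which require ML.
- A reader might think that a change of reference distribution is enough. The overlapping windows show that it may not be.

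The labels do not remove the point itself: the plan prescribes a specific reference distribution that is too liberal for this number of clinics, and a better one needs no extra data.

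**Conclusion.** The point holds as a minor correction. As written, the two over-time tests reject somewhat too often: 5.9% to 8.7% for the 2-df test and 5.5% to 6.6% for the trend test at a nominal 5%, across 20 to 28 clinics and the two covariance structures considered. These figures rest on the assumed 5% level, REML, equal weights, balanced arms, complete data and a correctly specified covariance. ML, or a random intercept fitted to serially correlated data, would make them larger. The primary comparison is a weighted linear regression of clinic change scores and is not affected.

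**What to change.** In Additional exploratory analyses:

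1. Replace both chi-square tests with small-sample F and t tests from a REML fit, using Kenward-Roger or Satterthwaite degrees of freedom, or use a permutation test.
2. Prespecify a covariance structure that allows serial correlation from the overlapping windows, for example unstructured over the three times.
3. State the significance level.

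For the mixed model in Sensitivity analyses, use the same small-sample references for the treatment-effect tests and intervals, and keep ML for the planned likelihood ratio comparison of stratum effects.

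The cost is a few sentences and no new data. There is a small statistical price. The critical value of the 2-df Wald statistic rises from 5.99 to 6.52 (20 clinics) or 6.35 (28) with a random intercept, and to 7.61 or 7.04 with an unstructured covariance. The latter also has six covariance parameters (three variances, three covariances) against two for a random intercept.

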### Usual Care Clinics

We will include PCORnet Datamarts participating in BP TRACK, a concurrently-running BP Control Registry within PCORnet that will provide quarterly datamart-level estimates of BP control and other aggregate metrics relevant to BP control. All participating datamarts will be included, with the following exceptions:

- We will exclude datamarts with any Active Clinics participating in BP MAP
- We will exclude datamarts that obscure dates via date-shifting, as this will not allow for control of concurrent secular trends

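### The 83% and 92% power stated for Full Support vs Self-Guided fits a threshold of 0.05; at the plan's own 0.04 it is about 79% and 90%, and the higher power claimed against Usual Care is not shown at 0.005

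*Combined protocol and SAP*

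**What the plan says.** The paragraph on sample size and power takes an SD of change in the control rate of 4.4 points from 16 pilot clinics. It continues "Assuming negligible change in the Self-Guided arm" and concludes that "we will have 83% power to detect a difference in differences of 6% in the BP control rate (or 92% power for 7% difference") with 10 clinics in each arm, adding that simulations confirmed this. No alpha, sidedness or formula is given.

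The section on primary hypothesis tests divides the 5% error rate: "In order to maintain an overall type 1 error rate of 5%, we will set our critical p-value threshold for Test 1 at" 0.04, with 0.005 for each comparison with Usual Care, "since they will benefit from the very large sample size expected in the Usual Care groups".

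On those two comparisons the power paragraph says only: "Power will be higher for comparisons of the Self-Guided and Full-Support groups with the large Usual Care comparison group in PCORnet under similar effect-size" assumptions. Usual Care data arrive as "quarterly datamart-level estimates of BP control", and the Analysis Plan normalises the weights to the "number of included clinics plus the number of participating PCORnet datamarts for the comparisons of each Arm with Usual Care". The Usual Care unit of analysis is therefore the datamart.

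The Randomization section plans to "randomize 10-14 Active Clinics to the Full Support Arm and 10-14 Active Clinics to the Self-Guided Arm".

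**The concern.** A power figure describes a test only at the threshold that test will use. The plan spends 0.01 of its alpha on the Usual Care comparisons, which leaves 0.04 for the randomised one. The stated power looks as if it was computed before that split. If so, a reader weighing a null result in the randomised comparison would credit the trial with slightly more power than it has at its minimum size.

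The Usual Care statement raises a separate question. A threshold of 0.005 is eight times stricter than 0.04, and the active side of each comparison may still be only 10 clinics. A comparator with very many patients is not necessarily one with many units. Whether the larger comparator outweighs the stricter threshold depends on the number of datamarts and on how much their change scores vary.

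For Self-Guided vs Usual Care there is a further difficulty. With negligible change assumed in the Self-Guided arm, an effect similar to the 6 points used for Test 1 would require Usual Care to move by about 6 points. The plan states no such expectation.

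**Working it through.** **Inputs from the documents.** SD of clinic-level change 4.4 points, differences of 6 and 7 points, 10 clinics per arm (Sample size and power); thresholds 0.04 and 0.005 (Primary hypothesis tests); linear regression on the clinic change scores (Analysis Plan), which with 20 clinics gives a t-test on 18 df.

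**Assumptions.** Two-sided test; SD 4.4 in both arms; no weighting, because cluster sizes are not given.

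**Formula.** SE = 4.4 × √(2/n), df = 2n − 2, noncentrality = difference / SE. Power is the noncentral t probability beyond ± the critical value.

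**Step 1: the plan's own figures.** For n = 10, SE = 4.4 × √0.2 = 1.968. The noncentrality is 6/1.968 = 3.05 and 7/1.968 = 3.56. At alpha 0.05 the critical value is 2.101 and power is **82.2% and 92.0%**. An SD of 4.36 to 4.38, which prints as 4.4, gives 83% and 92% to the nearest percent.

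**Step 2: the plan's threshold.** At alpha 0.04 the critical value rises to 2.214.

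| Clinics per arm | SE | df | Power, 6 points | Power, 7 points |
|---|---|---|---|---|
| 10 | 1.968 | 18 | 79.2% | 90.1% |
| 11 | 1.876 | 20 | 83.5% | 93.0% |
| 14 | 1.663 | 26 | 92.0% | 97.6% |

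With 10 per arm the shortfall is 83 − 79.2 = 3.8 points and 92 − 90.1 = 1.9 points. A simulation of the unweighted 10 vs 10 t-test (400,000 runs) gave 79.2% and 90.2% at 0.04, and 82.2% and 92.0% at 0.05.

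**Step 3: sensitivity to the SD.** Over 4.35 to 4.45, all of which print as 4.4, power for 6 points at 0.04 runs from 80.1% down to 78.3% and never reaches 83%. If the Full Support SD is 4.4 and the Self-Guided SD is taken as 4.0 or 5.0 (an assumed range), SE = √((4.4² + SD²)/10) and power is 82.8%/92.6% or 73.4%/85.8%.

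**Step 4: Usual Care at 0.005.** For 10 clinics against N datamarts, SE = √(4.4²/10 + SD²/N), df = 8 + N, difference 6 points. N and the datamart SD are assumptions, since the documents give neither. With a datamart SD of 4.4:

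| Datamarts | 10 | 20 | 30 | 40 | 50 | 100 |
|---|---|---|---|---|---|---|
| Power | 46% | 68% | 77% | 81% | 84% | 89% |

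Smallest number of datamarts for which power exceeds that of Test 1:

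| Assumed datamart SD | To exceed 79.2% (recomputed) | To exceed 83% (stated) |
|---|---|---|
| 2 | 13 | 18 |
| 3 | 21 | 28 |
| 4.4 | 35 | 46 |
| 6 | 56 | 74 |

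**The case against.** **The alpha is inferred.** A normal approximation at 0.04 gives 84.0% and 93.4%, about 1 point from the stated figures, so the sponsor may have used the right threshold with a rougher formula. This stands as a caution about how the figures arose. The t-test at 0.05 fits better: no SD that prints as 4.4 yields 83% and 92% under the normal approximation at 0.04. The plan's CDRN interaction figure (80% power for 12 points, 5 clinics per cell) also fits a t calculation at 0.05 (81.6%) better than a normal approximation (86.2% at 0.05, 84.0% at 0.04). Either way, a normal approximation overstates power for a regression on 20 clinics.

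**The gap is small.** This is true. One more clinic per arm removes it, and plausible variation in the Self-Guided SD moves power more than the change in alpha does. It limits the weight of the point but does not make the printed figures right for the 10 per arm to which they are attached.

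**The weights are not modelled.** This also stands. The 79% and 90% are unweighted approximations, and the documents do not show whether the confirming simulations used weights.

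**The Usual Care statement is qualitative and may be true.** This is fair. The plan calls that group large, the 10-datamart case is the least favourable shown, and large datamarts may vary less than single clinics. The criticism is only that the reader cannot check the statement.

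**Conclusion.** The point holds. At the plan's own threshold and minimum size, the randomised primary comparison has about 79% power for 6 points and 90% for 7 points, not 83% and 92%. This rests on a two-sided unweighted t-test with SD 4.4 in both arms. That the stated figures were computed at 0.05 is an inference from fit, but the restated power does not depend on it. The planned range of clinics absorbs the loss as soon as 11 per arm are randomised, so the design is not in question.

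The assertion of higher power against Usual Care is unsupported rather than wrong. At 0.005 it could be true or false, depending on two quantities the documents omit. For Test 2 the effect size is also unexplained.

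**What to change.** - State the alpha and sidedness behind the power figures.
- Restate Test 1 power at two-sided 0.04 with SD 4.4 in both arms: about 79% (6 points) and 90% (7 points) with 10 clinics per arm, 83% and 93% with 11, 92% and 98% with 14. Label these as unweighted, or rerun the simulations at 0.04 with the planned weights if cluster sizes are known.
- Replace the general statement on Usual Care with the power at 0.005 for the expected number of BP TRACK datamarts and a stated SD of their change.
- For Self-Guided vs Usual Care, state the effect size assumed and the Usual Care change behind it, consistent with the negligible change assumed in the Self-Guided arm.

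The cost is wording only. The design and clinic numbers do not change; the printed Test 1 figures for 10 per arm fall by about 4 and 2 points.
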